2.0 Goals

2.1 Primary Goal

To determine response rates (>=PR) of prospectively treated MM patients with one cycle of therapy containing a combination of an immunomodulator and dexamethasone.

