7.0 Protocol Treatment

7.1 Treatment Schedule

Cohort A and B Cycle 1

Treatment medication table. Patient may receive Lenalidomide OR Lenalidomide + Dexamethasone.

Agent	Dose Level	Route	Day	Re Rx
Lenalidomide	25 mg*	Oral	Cycle 1: Day 1-14	Cycle 1: 21 days
Dexamethasone	40 mg**	Oral	Cycle 1: Day 1 ,8, ,15	Cycle 1: 21 days

Cycle 1 length = 21 days

* Starting dose will be determined as per the creatine clearance below (see 7.12)

**The dose of dexamethasone used can be determined by the treating physician and omitted if needed.

Cohort C and D Cycle 1

Treatment medication table. Patient may receive Lenalidomide + Dexamethasone OR Pomalidomide + Dexamethasone.

Agent	Dose Level	Route	Day	ReRx
Lenalidomide	25 mg*	Oral	Cycle 1: Day 1-14	Cycle 1: 21 days
Pomalidomide	4 mg	Oral	Cycle 1: Day 1-21	Cycle 1: 21 days
Dexamethasone	40 mg**	Oral	Cycle 1: Day 1 ,8, ,15	Cycle 1: 21 days

Cycle 1 length = 21 days

* Starting dose will be determined as per the creatinine clearance below (see 7.12)

** The dose of dexamethasone used can be determined by the treating physician and omitted if needed.

Cohort A and B Cycles 2-6

Treatment Medication Table. Patient may receive Lenalidomide based regimens.

Agent	Dose Level	Route	Day	Re Rx
Lenalidomide	25 mg*	Oral	Cycle 2-6: Day 1-21	Cycles 2-6: 28 days
Dexamethasone	40 mg**	Oral	Cycle 2-6: Day 1 ,8, ,15, 22	Cycles 2-6: 28 days

Note: Standard of care agents can be added for cycles 2-6 as long as the regimen contains lenalidomide

Cycles 2-6 length = 28 days

* Any dose-adjustments will be determined as per the creatine clearance below (see 7.12).

** The dose of dexamethasone used can be determined by the treating physician and omitted if needed.

Cohort C and D Cycles 2-6

Treatment medication table. Patient may receive Lenalidomide based regimen OR Pomalidomide based regimen.

Agent	Dose Level	Route	Day	ReRx
Lenalidomide	25 mg*	Oral	Cycles 2-6: Day 1-21	Cycles 2-6: 28 days
Pomalidomide	4 mg	Oral	Cycles 2-6: Day 1-21	Cycles 2-6: 28 days
Dexamethasone	40 mg**	Oral	Cycle 2-6: Day 1,8,15,22	Cycles 2-6: 28 days

Note: Standard of care agents can be added for cycles 2-6 as long as the regimen contains lenalidomide or pomalidomide

Cycles 2-6 length = 28 days

* Any dose-adjustments will be determined as per the creatinine clearance below (see 7.12).

** The dose of dexamethasone used can be determined by the treating physician and omitted if needed.

7.12

Creatinine Clearance (CrCl)	Lenalidomide Dose

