Vascular disorders	Thromboembolic event \geq Grade 3		
 • Omit dose and start anticoagulation; restart at investigator's discretion (maintain dose level)
Immune system disorders	Allergic reaction Grade 2-3		
 • Omit dose and follow at least weekly until resolution • If AE resolves to \leqGrade 1, reduce dose level and continue therapy
	Anaphylaxis Grade 4		
 • Discontinue study treatment and go off study
Skin and subcutaneous tissue disorders	Erythema multiforme \geq Grade 3		Discontinue study treatment and go off study
	Skin ulceration \geq Grade 2		Discontinue study treatment and go off study
	Other: Non-blistering rash Grade 3		
 • If Grade 3 omit dose and follow weekly until resolution • If AE resolves to \leqGrade 2 continue therapy
Other AEs	Other: Non-blistering rash Grade 4		
 • Discontinue study treatment and go off study
	Non-hematologic AE assessed as related to lenalidomide \geq Grade 3		
 • Omit dose and follow at least weekly until resolution • If the AE resolves to \leqGrade 2, implement one dose reduction step and continue therapy (per Table 8.1)

* Located at http://ctep.cancer.gov/protocolDevelopment/electronic_applications.ctc.htm

** Use the following to describe actions in the Action column:

- **Omit** = The current dose(s) for the specified drug(s) during a cycle is skipped. The patient does not make up the omitted dose(s) at a later time
- **Hold/Delay** = The current dose(s) of all drugs during a cycle is delayed. The patient does make up the delayed dose(s) when the patient meets the protocol criteria to restart drugs.
- **Discontinue** = The specified drug(s) are totally stopped.

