11.1 Terms and definitions

- **M-protein:** synonyms include M-spike, monoclonal protein and myeloma protein, paraprotein, M-component.

Serum M-protein level is quantitated using densitometry on SPEP except in cases where the SPEP is felt to be unreliable.

- M-proteins migrating in the β -region (usually IgA M-proteins)
- Cases in which the M-protein is so large and narrow on agarose (some specimens >4 g/dL) that they underestimate the actual immunoglobulin level (by greater than 1500 mg/dL) due to technical staining properties of the agarose gel.
- Cases in which there are multiple peaks of same M-protein (aggregates or dimers)

If SPEP is not available or felt to be unreliable (above examples) for routine M-protein quantitation, then quantitative immunoglobulin levels derived from nephelometry or turbidometry can be accepted, with the exception that quantitative IgG may not be used. However, this must be explicitly reported at baseline, and only nephelometry can be used for that patient to assess response. SPEP derived M-protein values and quantitative nephelometric immunoglobulin values cannot be used interchangeably.

Urine M-protein measurement is estimated using 24-h UPEP only. Random or 24 h urine tests measuring kappa and lambda light chain levels are not reliable and are not recommended.

FLC estimation is currently carried out using the serum FLC assay (Freelite, The Binding Site Limited, UK). Patients with kappa/lambda FLC ratio <0.26 are defined as having monoclonal lambda FLC and those with ratios >1.65 as having a monoclonal kappa FLC. The monoclonal light chain isotype is considered the involved FLC isotype, and the opposite light chain type as the unininvolved FLC type.

- **Response terms:** The following response terms will be used: stringent Complete Response (sCR), complete response (CR), very good partial response (VGPR), partial response (PR), Minimal Response (MR), stable disease (SD), and progressive disease (PD).

In addition, for each response category, there will be an “unconfirmed” response category, which will be for internal use, for the purpose of guiding decision making and test ordering. These designations will be applied at the time of the first measurement at which the quantitative aspect of the response category has been satisfied without the confirmation step having been satisfied. The designation “u” will precede the standard abbreviations, and will include usCR, uCR, uVGPR, uPR, uMR, uPD.

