16.0 Statistical Considerations and Methodology

16.1 Overview:

This is a pilot study to determine the response rates (>PR) of the combination of an immunomodulator and dexamethasone in Multiple Myeloma (MM) patients of each clinically relevant biomarker. This combination will be evaluated in four cohorts: Cohort A (Smoldering MM), Cohort B (Newly Diagnosed MM), Cohort C (Relapsed/Refractory MM) and Cohort D (Relapsed on Len maintenance). This study will not utilize a formal statistical design but will focus more on estimation rather than hypothesis testing.

16.11 Primary Endpoint: The primary endpoint of this trial is to estimate (>PR) response rates (RR) after one cycle of treatment. Biomarkers of interest will be identified and categorized into clinically relevant groups (e.g. positive vs. negative) by evaluating baseline and post treatment (after cycle one) biospecimens. RR will be estimated within each biomarker.

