16.2 Statistical Design

Due to the lack of data to identify relevant biomarkers, the estimation of RR would be of interest. In each group, the response rates will be examined to see if there's any preliminary evidence to suggest further studies. This study will not utilize a formal statistical design.

For each biomarker category, the RR will be estimated by the number of patients who achieve a PR or better divided by the total number of evaluable patients in each cohort. Exact binomial 95% confidence intervals for these rates will be calculated.

16.22 Sample Size: A maximum of 30 evaluable patients will be accrued in cohort A and B and 60 patients in cohort C and D respectively. We anticipate accruing an additional 2 in cohort A and B and 3 in cohort C and D to account for ineligibility, cancellation, major treatment violation, or other reasons. Therefore, the maximum projected accrual is 190 patients (A: 32, B: 32, C: 63 and D: 63).

16.23 Accrual Rate and Study Duration: The anticipated accrual rate is 6 evaluable patients per month. Therefore, the accrual period for this pilot study is expected to be approximately 32 months. The final analysis can begin approximately 35 months after the trial begins, i.e. as soon as the last patient has been observed for 1 months and allowing 2 months for data entry.

16.24 Other considerations: Adverse events, quality/duration of response, and patterns of treatment failure observed in this study, as well as scientific discoveries or changes in standard care will be taken into account in any decision to terminate the study

16.3 Analysis Plan.

The analysis for this study is planned to start after data maturity has occurred. It is anticipated that the earliest date in which the result will be available via manuscript, abstract or presentation after the last registered patient has been followed for at least 1 month.

16.31 Primary Outcome Analyses:

Each cohort (A-D) will be evaluated separately and independently.

16.311 Definition:

The primary endpoint of this study is RR after 1 cycle of treatment. RR is defined as a binary variable. A success will be defined as patient who achieve a response of a PR or better using the IMWG criteria (Section 11.0) after one cycle of treatment. All patients meeting eligibility criteria who have signed a consent form, who complete at least one cycle of treatment and have successfully submitted biospecimens (pre and post treatment) will be evaluable for the endpoint.

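### Section 16.311 leaves treated patients who die or stop in cycle 1 out of the cohort response rate, and no all-treated rate is planned beside it

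*Combined protocol and SAP*

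**What the plan says.** Section 2.1 gives the primary goal: "To determine response rates (>=PR) of prospectively treated MM patients with one cycle of therapy containing a combination of an immunomodulator and dexamethasone". Section 16.11 begins in the same vein, "The primary endpoint of this trial is to estimate (>PR) response rates (RR) after one cycle of treatment" (16.311 makes clear that a PR itself is a success), and then turns to subgroups: "RR will be estimated within each biomarker".

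Section 16.311 fixes who counts. The set is eligible, consented patients "who complete at least one cycle of treatment and have successfully submitted biospecimens (pre and post treatment) will be evaluable for the endpoint". Section 16.2 and the Estimation paragraph after 16.311 use this set as the only RR denominator, with exact binomial 95% intervals. The secondary analyses in 16.32 name no other set.

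Section 16.22 targets 30 evaluable patients in each of cohorts A and B and 60 in each of C and D. It adds 2 and 3 per cohort "to account for ineligibility, cancellation, major treatment violation, or other reasons". Under 13.1, a patient who leaves treatment before six cycles is not followed further. Under 13.6, a cancelled patient is one who was never treated.

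**The concern.** A patient who starts treatment and then dies, or stops for toxicity, in the first three weeks has not responded to that cycle. Under 16.311 the patient is not scored as a failure but leaves the calculation, and 16.22 covers the loss by extra accrual. Nothing in the plan counts such patients as non-responders or reports a rate that includes them.

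The paired-specimen condition has a clear purpose for RR within biomarker groups, because patients are to be classified from baseline and post-cycle-1 samples. It has no such purpose for the plain cohort RR, where it also removes patients who finished cycle 1 with a known response but lack a sample.

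What is at stake is the meaning of the headline number. In an estimation study the rate and its denominator are the product, and 16.2 will use the rates to look for evidence that supports further studies.

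**Working it through.** **Inputs.** From 16.22: evaluable targets 30, 30, 60, 60; allowances 2, 2, 3, 3. The documents give no expected cycle-1 RR and no cycle-1 loss rate. I therefore assume an RR of 30%, 50% and 70%, and take the plan's allowance as the loss.

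**The plan's own figure.** (30+2) + (30+2) + (60+3) + (60+3) = 190, which matches the stated maximum accrual.

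**Formula.** Let q be the share of treated eligible patients who are excluded, RR the reported evaluable-set rate, and r the response rate among the excluded. The all-treated rate is RR x (1 - q) + r x q, so

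shift = reported - all-treated = q x (RR - r).

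If every excluded patient is a non-responder (r = 0), the shift is RR x q, its ceiling. If every excluded patient is a responder (r = 1), it is -(1 - RR) x q.

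**At the planned allowance** (percentage points):

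| Reported RR | A/B, q = 2/32 = 0.0625: r = 0 / r = 1 | C/D, q = 3/63 = 0.0476: r = 0 / r = 1 |
|---|---|---|
| 30% | +1.9 / -4.4 | +1.4 / -3.3 |
| 50% | +3.1 / -3.1 | +2.4 / -2.4 |
| 70% | +4.4 / -1.9 | +3.3 / -1.4 |

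The r = 0 entries apply to early failures. Negative entries are possible only for patients excluded for another reason, mainly a missing specimen.

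**In counts, with exact (Clopper-Pearson) 95% intervals:**

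- A/B: 15/30 = 50.0% (31.3-68.7) against 15/32 = 46.9% (29.1-65.3) if both excluded patients failed, or 17/32 = 53.1% (34.7-70.9) if both responded.
- C/D: 30/60 = 50.0% (36.8-63.2) against 30/63 = 47.6% (34.9-60.6) or 33/63 = 52.4% (39.4-65.1).

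**Against the precision.** Half-widths at 50% are (68.7 - 31.3)/2 = 18.7 and (63.2 - 36.8)/2 = 13.2 points. The ceiling is 3.1/18.7 = 0.17 and 2.4/13.2 = 0.18 of these.

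**Losses needed for a 5-point shift at 50%.**

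- On top of a full evaluable set, 4 failures give 15/34 = 44.1% (shift 5.9; 3 give 15/33, shift 4.5). In C/D, 7 failures give 30/67 = 44.8% (shift 5.2; 6 give 30/66, shift 4.5). The totals 34 and 67 exceed the accrual maxima of 32 and 63.
- Within those maxima the counts are the same: 14/28 = 50.0% against 14/32 = 43.8%, and 28/56 = 50.0% against 28/63 = 44.4%.
- Both counts exceed the planned allowance of 2 and 3.

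**The case against.** The best defence is that section 16 is mostly about biomarkers. Section 16.1 and the RR formulas in 16.2 and the Estimation paragraph are tied to biomarker groups, and a patient without a post-cycle-1 sample cannot be classified. That stands, and it is why the paired-specimen set should stay for those analyses. It does not cover the overall RR in 2.1 and the opening of 16.11.

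A second defence is that the affected group is narrow. Cycle 1 lasts 21 days, and section 4.0 schedules no disease assessment between Day 1 and the pre-cycle-2 visit. That stands too.

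Several stronger readings are tempting but unsupported:

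- *Progressors are dropped.* Progression found at the pre-cycle-2 visit, in a completer with both specimens, stays in as a non-response. Only those who leave before finishing the cycle are lost.
- *Goal 2.1 contradicts 16.311.* The goal can be read as all treated patients or as those who got through one cycle. It is ambiguous, not contradictory.
- *Completion is left wholly open.* The meaning of an omitted dose is given ("The patient does not make up the omitted dose(s) at a later time"), the cycle length is fixed, and 13.5 provides a category for severe cycle-1 departures. The point does not rest on this.
- *The losses will be hidden.* The plan does not promise a listing of exclusions, but 13.2 to 13.6 define the categories and nothing prevents one.

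**Conclusion.** The point holds as a cheap improvement. The only planned cohort RR is conditional on finishing cycle 1 and giving both specimens, so treated early failures are left out and no all-treated RR shows their effect.

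If the whole allowance were treated early failures, the overstatement would be at most 1.9-4.4 points in A/B and 1.4-3.3 points in C/D, for an RR of 30-70%. This is an upper figure at that allowance, because the allowance also covers ineligible and never-treated patients. At 50% it is under a fifth of the CI half-width, and no decision threshold depends on the RR.

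A reader might infer that the reported RR is biased upward overall. The documents do not support that, since excluding completers who lack only a specimen can shift it either way. A reader might also assume 10-20% early loss and arrive at about 3-15 points. The documents give no loss rate, and losses of that size exceed the plan's allowance.

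**What to change.** In 16.311, add for each cohort an overall RR with an exact 95% CI:

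- **Denominator:** all eligible patients who received at least one cycle-1 dose.
- **Responder:** the PR threshold is met at the pre-cycle-2 assessment, or at the end-of-treatment assessment for a patient who stops in cycle 1, before any added or new agent. The last condition is needed because "Standard of care agents can be added for cycles 2-6 as long as the regimen contains lenalidomide", with a matching note for pomalidomide in C and D.
- **No such assessment:** count a treated patient as a non-responder.
- **Confirmation:** treat it exactly as for the evaluable-set RR, and do not require a second determination inside the cycle-1 window. Section 4.0 schedules only one post-treatment M-protein assessment there, while 11.2 and footnote a of Table 11.5 ask for two consecutive ones. Section 11.1 describes the unconfirmed category as one "which will be for internal use, for the purpose of guiding decision making and test ordering". Requiring both values by the pre-cycle-2 visit could turn completers as well as early stoppers into non-responders.

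Keep the paired-specimen set, and the 30 and 60 targets in 16.22, for the RR within biomarker groups and the biomarker analyses. Report both rates, and list excluded treated patients by reason (died, stopped, progressed, no specimen, major violation).

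The cost is a text change to the analysis sets in 16.311, with a clarifying line in 16.22. It needs no new visits or tests. The overall RR may come out slightly lower, and it will be somewhat conservative for early stoppers with no assessment.

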16.32 Secondary Outcome Analyses

16.321 Biomarkers and RR will be analyzed using logistic regressions to identify predictive biomarkers.

16.322 RR among African American (AA) patients and white MM patients will be evaluated after one cycle of treatment. Chi-Square (or Fischer Exact) test and 95% confidence intervals will be estimated to compared AA and white patients descriptively.

16.323 Correlation between the depth of hematological responses and biomarkers will be estimated. Logistic regressions and chi square (or Fischer exact) testing will be utilized.

16.33 Data & Safety Monitoring:

The principal investigator(s) and the study statistician will review the study at least twice a year to identify accrual, adverse event, and any endpoint problems that might be developing. The Mayo Clinic Cancer Center (MCCC) Data Safety Monitoring Board (DSMB) is responsible for reviewing accrual and safety data for this trial at least twice a year, based on reports provided by the MCCC Statistical Office.

Adverse Event Stopping Rules: (Each cohort will be analyzed separately) The stopping rules specified below are based on the knowledge available at study development. We note that the Adverse Event Stopping Rule may be adjusted in the event of either (1) the study re-opening to accrual or (2) at any time during the conduct of the trial and in consideration of newly acquired information regarding the adverse event profile of the treatment(s) under investigation. The study team may choose to suspend accrual because of unexpected adverse event profiles that have not crossed the specified rule below.

Accrual will be temporarily suspended to this study if at any time we observe events considered at least possibly related to study treatment (i.e. an adverse

event with attribute specified as “possible”, “probable”, or “definite”) that satisfy either of the following:

- If 3 or more out of the first 10 treated patients experience grade 4+ non-hematological toxicities
- If after the first 10 patients have been treated, 30% of patients experience grade 4+ non-hematologic toxicities

We note that we will review grade 5 adverse events deemed “unrelated” or “unlikely to be related”, to verify their attribution and to monitor the emergence of a previously unrecognized treatment-related adverse event.

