Pomalidomide: This third generation IMiD was approved for the treatment of relapsed/refractory myeloma in 2013 for patients who had received at least two prior regimens including lenalidomide and bortezomib. This agent has only been evaluated in the previously treated setting. In one phase II study, the combination of pomalidomide and dexamethasone where the pomalidomide was dosed at 2 mg daily had a 63% overall response rate including 40% ORR in lenalidomide-refractory patients and 37% ORR in thalidomide-refractory patients(17). In another study which included only lenalidomide-refractory patients, the overall response rate was 47%(18). An alternative dosing strategy of 4 mg daily for 21 out of 28 days was also explored and the ORR was 35–42% (19, 20).

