1.2 Rationale for the current trial

Current treatment regimens in both the upfront and relapsed settings have trended towards utilizing combination therapies that include a combination of an IMiD with proteasome inhibitors and/or monoclonal antibodies(21, 22). This is largely due to the results of several phase III clinical trials demonstrating the overall benefit of three-drug regimens (triplets) containing IMiDs and proteasome inhibitors or IMiDs and monoclonal antibodies over two-drug regimens (doublets) containing IMiDs alone with dexamethasone in terms of their depth and duration of hematological response. However, some patients within these clinical trials as well as in real-world clinical practice may derive equal depth and duration of therapeutic response to two-drug regimens (doublets) containing IMiDs alone with dexamethasone compared to triplets. At this time, our gap in knowledge prevents us from *apriori* identifying those patients who can be spared the physical and financial toxicity of adding the additional third or fourth agent such as proteasome inhibitors and/or monoclonal antibodies to an IMiD and dexamethasone. Being able to develop and validate biomarkers capable of filling this fundamental gap of knowledge could have practical implications to the clinical care of patients with MM. **As such, this study will provide the possibility of obtaining biospecimens from untreated smoldering MM and MM patients as well as previously treated MM patients pre- and post-treatment with one cycle of therapy containing only an IMiD and dexamethasone.**

Furthermore, it has been long hypothesized that there may be a differential response to IMiDs for patients belonging to African American (AA) race. Small studies have suggested that AA patients may have a better response to IMiDs than whites but receive a lesser access to these agents. This has led to the need for a more definitive testing to develop an efficacy profile as well as biomarker identification which may help predict the differences in response among AA and white patients with MM.

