2.2 Secondary Goals

1. To identify biomarkers that predict response rates of untreated smoldering MM and MM patients to a combination of an immunomodulator and dexamethasone.
2. To compare response rates of MM among AA and white patients to a combination of an immunomodulator and dexamethasone.
3. To establish correlation of biomarkers in treated MM patients with the combination of an immunomodulator and dexamethasone to the depth of hematological response observed in new or previously treated patients.

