3.0 Registration Patient Eligibility

3.1 Registration - Inclusion Criteria

3.11 Age \geq 18 years

3.12 **Cohort A:** Patient must have untreated smoldering multiple myeloma which is defined by the presence of 10% or more but less than 60% clonal plasma cells in the bone marrow and the absence of any of the following myeloma related symptoms or laboratory and radiographic abnormalities: anemia, hypercalcemia, renal insufficiency, hypercalcemia, serum free light chain ratio of greater than 100 or more than one focal marrow multiple myeloma lesion on MRI imaging.

Cohort B: Patient must have newly diagnosed myeloma requiring treatment and no prior therapies

Cohort C: Patient must have relapsed or refractory multiple myeloma with at least one prior therapy for their multiple myeloma but not refractory to all IMiDs

Cohort D: Patient must have relapsed or refractory multiple myeloma with Lenalidomide as part of a maintenance regimen as their most recent therapy

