16.4 Inclusion of Women and Minorities

16.41 This study will be available to all eligible patients, regardless of race, gender, or ethnic origin.

16.42 There is no information currently available regarding differential effects of this regimen in subsets defined by race, gender, or ethnicity, and there is no reason to expect such differences to exist. Therefore, although the planned analysis will, as always, look for differences in treatment effect based on racial and gender groupings, the sample size is not increased in order to provide additional power for subset analyses.

16.43 Based on prior studies involving similar disease sites, we expect about 3-5% of patients will be classified as minorities by race. However, we are aiming to increase these percentages and accrue 15% of African American patients to meet our secondary endpoints. If efforts to accrue in this racial category are not fruitful, the study will continue to accrue patients in the other racial categories. . Expected sizes of racial by gender subsets are shown in the following table:

Accrual Estimates by Gender/Ethnicity/Race

Ethnic Category	Sex/Gender			
	Females	Males	Unknown	Total
Hispanic or Latino	0	6	0	6
Not Hispanic or Latino	64	120	0	184
Unknown	0	0	0	0
Ethnic Category: Total of all subjects	64	125	0	190
Racial Category				
American Indian or Alaskan Native	0	0	0	0
Asian	0	0	0	0
Black or African American	9	20	0	29
Native Hawaiian or other Pacific Islander	0	0	0	00
White	56	105	0	161
More than one race	0	0	0	0
Unknown	0	0	0	0
Racial Category: Total of all subjects	64	125	0	190

Ethnic Categories: **Hispanic or Latino** – a person of Cuban, Mexican, Puerto Rican, South or Central American, or other Spanish culture or origin, regardless of race. The term “Spanish origin” can also be used in addition to “Hispanic or Latino.”

Not Hispanic or Latino

Racial Categories: **American Indian or Alaskan Native** – a person having origins in any of the original peoples of North, Central, or South America, and who maintains tribal affiliations or community attachment.

Asian – a person having origins in any of the original peoples of the Far East, Southeast Asia, or the Indian subcontinent including, for example, Cambodia, China, India, Japan, Korea, Malaysia, Pakistan, the Philippine Islands, Thailand, and Vietnam. (Note: Individuals from the Philippine Islands have been recorded as Pacific Islanders in previous data collection strategies.)

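### The crude AA-white response comparison in 16.322 is open to confounding by prior IMiD history, plausibly in favour of AA patients, and should be reported by that history

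*Combined protocol and SAP*

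**What the plan says.** Secondary goal 2 in Section 2.2 is "To compare response rates of MM among AA and white patients to a combination of an immunomodulator and dexamethasone". Section 16.322 carries it out: "RR among African American (AA) patients and white MM patients will be evaluated after one cycle of treatment", with a chi-square or Fisher "test and 95% confidence intervals will be estimated to compared AA and white patients descriptively". It names no covariate, stratifier or cohort. Separate evaluation of each cohort is stated in 16.31, under the primary analyses, and is not repeated in 16.322.

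Four other places bear on the comparison:

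- Section 1.2: "Small studies have suggested that AA patients may have a better response to IMiDs than whites but receive a lesser access to these agents".
- Section 3.12 admits to Cohort C patients "with at least one prior therapy for their multiple myeloma but not refractory to all IMiDs". Cohorts A and B are untreated. In Cohort D every patient had lenalidomide maintenance as the latest therapy.
- Section 1.1 reports that pomalidomide with dexamethasone in one phase II study "had a 63% overall response rate including 40% ORR in lenalidomide-refractory patients", and 37% in thalidomide-refractory patients. A second study, of lenalidomide-refractory patients only, had 47%.
- Section 12.1 records prior treatment only as a count (0, 1, 2, 3 or more).

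Section 16.42 says "There is no information currently available regarding differential effects of this regimen in subsets defined by race, gender, or ethnicity" and adds that no such differences are to be expected.

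**The concern.** One sentence in 1.2 supplies both the hypothesis (better response in AA patients) and a possible alternative explanation for it (less earlier access to the drug class). If less access means that fewer AA patients in Cohort C are IMiD-refractory, they could respond more often for that reason alone. A two-by-two test cannot tell the two explanations apart. Analysis by cohort would deal with differences between cohorts, but not with an imbalance inside Cohort C, the one cohort whose entry criterion allows IMiD status to run from naive to partly refractory.

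At stake is the reading of secondary goal 2: an observed difference in the hypothesised direction could be put down to race, and biomarker work planned on it, when it reflects treatment history.

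Section 16.42 is a separate matter of wording. It denies both the evidence and the expectation on which 1.2 and goal 2 rest, while 16.43 sets a 15% AA accrual target to serve the secondary endpoints.

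**Working it through.** **The plan's own figures.** 32 + 32 + 63 + 63 = 190 maximum accrual. 15% of 190 = 28.5, shown as 29 AA in the 16.43 table, and 29 + 161 white = 190. These reproduce. Section 16.322 states no power or effect size, so there is no design calculation to check. Cohort C has 60 evaluable patients; 15% is 9 AA, leaving 51 white.

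**Model.** Assume no race effect. Let r0 be the response rate in IMiD-refractory patients, r1 the rate in the others, and f the refractory share in a race group. Then

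RR = r1(1 − f) + r0 f, and the spurious difference (AA − white) = (f_white − f_AA)(r1 − r0).

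**Inputs.**

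- r0: 40% and 47%, from 1.1; 37% is also given there.
- r1: 63% as a low value, because the 63% overall rate already includes refractory patients; 75% is an assumed upper value.
- f: assumed throughout, because no document gives it by race.
- The 1.1 rates are not one-cycle rates; the gap between them is assumed to carry over to cycle 1.

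**Results** for 9 v 51. The last two columns are the probability of a result significant at two-sided 5% with AA better, by exact enumeration; chi-square is without continuity correction.

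| r0 / r1 | refractory, white / AA | RR, AA v white | difference (points) | chi-square | Fisher |
|---|---|---|---|---|---|
| 47 / 63% | 50 / 30% | 58.2 v 55.0% | +3.2 | 3.4% | 2.0% |
| 40 / 63% | 50 / 30% | 56.1 v 51.5% | +4.6 | 4.2% | 2.5% |
| 40 / 63% | 60 / 30% | 56.1 v 49.2% | +6.9 | 5.5% | 3.4% |
| 40 / 75% | 60 / 30% | 64.5 v 54.0% | +10.5 | 7.6% | 4.8% |
| 47 / 75% | 70 / 20% | 69.4 v 55.4% | +14.0 | 10.6% | 7.0% |
| 40 / 75% | 70 / 20% | 68.0 v 50.5% | +17.5 | 15.2% | 10.3% |
| 40 / 63% | 50 / 50% | 51.5 v 51.5% | 0 | 2.4% | 1.4% |
| 40 / 63% | 50 / 70% | 46.9 v 51.5% | −4.6 | 1.3% | 0.7% |

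Example: (0.70 − 0.20)(0.75 − 0.40) = 0.175. With equal true rates the false AA-better probability is 2.1-2.6% by chi-square and 1.3-1.5% by Fisher, depending on the common rate. Taking r0 = 37% raises the upper end to 0.50 × 0.38 = 19 points.

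The 95% interval for 9 v 51 has a half-width of about 33 to 35 points in all these cases.

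**Power in IMiD-naive patients.** Cohorts A and B together have 60 evaluable patients, again 9 v 51 at 15%. If the true rates were 70% (AA) and 50% (white), chi-square would detect the difference about 19% of the time and Fisher about 13%.

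**The case against.** A reader might infer that the comparison is in fact biased toward an AA advantage, even within Cohort C. The documents do not support that:

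- Section 1.2 credits small studies and gives no size. Nothing shows that an access gap persists among patients who reach Cohort C, where those refractory to all IMiDs are already excluded.
- The access statement concerns exposure, whereas the response gap in 1.1 is for refractoriness. The lenalidomide ranges in 1.1 (48-61%, and 46-57% with thalidomide pretreatment in most patients) overlap heavily, so exposure alone may matter little.
- Cohort C may receive lenalidomide or pomalidomide. If that choice follows IMiD history, it could offset or change the bias.

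These points stand, and they limit the claim to plausible confounding of unknown size.

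It can also be said that 16.322 is labelled descriptive, that the study is an estimation pilot, and that an interval of about ±35 points swamps the illustrated bias. This lowers the stakes but does not answer the point. A significance test is still planned, the interval measures chance and not confounding, and a descriptive difference in the expected direction is what would prompt further work.

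The false-positive figures depend on the test. With 9 AA patients and response near 50%, expected counts fall below 5, where Fisher is the usual choice, so the lower column may be the relevant one. The 15% figure needs chi-square, the widest imbalance and the assumed 75% rate together.

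**Conclusion.** The gap is real. Section 16.322 takes no account of prior IMiD history, Section 12 does not capture it, 1.2 itself raises unequal access, and Cohort C allows the imbalance. The supportable statement is that the crude comparison is open to confounding, plausibly in favour of AA patients.

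Under the assumed refractory shares and rates, with no true race effect, the spurious advantage in Cohort C is about 3 to 18 points. The chance of a false finding for AA patients goes from about 2.3% to 3-15% (chi-square) or from about 1.3% to 2-10% (Fisher). All of this rests on assumed shares by race and on carrying the 1.1 rates over to one cycle. Equal shares remove the bias, and a more refractory AA group reverses its sign.

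The conflict between 16.42 and 1.2 needs no assumption, but it is an inconsistency of wording and not evidence of confounding.

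**What to change.** In 16.322, beside the crude result:

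1. Report the AA-white response difference with 95% CI (Mantel-Haenszel), stratified by cohort and, within Cohort C, by IMiD-refractory or not, with the definition of refractory stated.
2. Tabulate prior IMiD exposure and refractoriness by race.
3. Show the comparison in IMiD-naive patients (Cohorts A and B and the naive part of C) descriptively. Set no rule that absence of a difference there excludes a race effect; power of 13-19% for a 20-point difference would not support one.

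Reword 16.42 so that it agrees with 1.2 and secondary goal 2. Specify all of this before response by race is examined.

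The cost is SAP wording, one further estimate and one table. IMiD history must already be known to apply the Cohort C and D criteria, although Section 12 would need it added as a descriptor. The price is a somewhat wider interval and sparse strata: at a 20-30% refractory share, 9 AA patients in Cohort C give only 2 or 3 in the refractory stratum (1.8 to 2.7). A finer split by exposure would be too thin, and the stratified estimate should itself be read descriptively.
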